9.3 Analysis of Efficacy Endpoints

9.3.1 Primary Endpoint Analysis

Formal hypothesis testing and statistical analysis are not planned for this study. The primary efficacy endpoint data will be summarized descriptively for the control and treatment areas.

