4 STUDY DESIGN

This is a single-center, prospective, non-randomized, open-labeled study in approximately 14 subjects, age 24 to 60 years, who are scheduled for abdominoplasty, and will undergo one RF treatment in the abdominal region. Subjects will receive 1 RF treatment with the truSculpt device [REDACTED]

[REDACTED]

One treatment will be performed by the truSculpt device on one abdominal subarea, while the other abdominal subarea will not be treated and will serve as a control. Subjects will have incisional or full-thickness punch skin biopsies. Biopsies will be harvested from tissue to be removed during the abdominoplasty, and will subsequently be cultured. At least two biopsy samples for each subject will be obtained during the abdominoplasty: at least one from the treatment area and at least one from the control area. The purpose of the biopsies is to examine and compare potential histological changes in cutaneous and sub-cutaneous tissue levels that occur as a result of RF treatment.

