6.3 Biopsy Collection Visit

The Biopsy Collection visit will occur on the same day as the abdominoplasty surgery. The following procedures will be performed prior to and during abdominoplasty surgery:

1. Review of subject medical history.
2. Assess and record any additions, changes and/or deletions in prescription and nonprescription concomitant medications since the previous study visit.
3. Record severity and duration of any adverse device effects following RF treatment and assess for any new adverse device effects.
4. Biopsy collection procedure:
 - a. Refer to the patient chart and identify the RF treatment location.
 - b. During the biopsy collection procedure, at least one skin biopsy (approximately 10 mm x 10 mm; full thickness) will be taken from the area treated with RF; and at least one skin biopsy (approximately 10 mm x 10 mm; full thickness) will be taken from an equivalent contralateral non-treated area as a control.

c. Each biopsy sample will be immediately placed in the prepared fixative vials, making sure the samples are fully submerged in the solution. The vials will be labeled with the subject ID number, subject initials and biopsy date. The vials will be randomly numbered, and the numbers of the vials containing the biopsy from the RF treated and control skin will be recorded in the patient chart. The histologist will remain blinded to the nature of each biopsy sample (treatment or control).

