9.2 Analysis Sets

The efficacy analysis set will include all enrolled subjects who complete the RF treatment session using the study device.

The safety analysis set will include all subjects enrolled in the study who start the RF treatment session using the study device.

Missing data will not be imputed for efficacy or safety endpoints.

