9.4 Safety Analyses

Device-related and procedure-related adverse effects (AEs) and subjects who prematurely terminate from the study due to an adverse device effect, including the treatment-related pain ratings, will be tabulated and analyzed. For a given AE term, counting will be done by subject, not by event, i.e. for a subject reporting the same AE more than once; the event will be counted only once, at the most severe and longest duration. The number and percentage of subjects experiencing each AE Term will be descriptively summarized. Subject pain ratings during treatment will also be summarized descriptively.

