11.6 Data Collection, Record Keeping and Storage

The principal investigator is responsible for assuring that all study records including case report forms (CRFs), informed consent forms, device accountability records, source documents (e.g., medical records, histology reports etc.) and other study records are complete, accurate and recorded in a timely manner.

CRFs should not be the only record of a patient's participation in the study and will be used for transcribing data from source documents which are the point of first entry of data collected for each subject (with the exception of documents listed under **B**). The investigator or research staff at the site will ensure that:

A. Source documentation thoroughly and adequately documents:

1. That patient is participating in a clinical study and has been properly informed and consented prior to participation in the study,
2. Medical history,
3. Concomitant medications,
4. Patient's condition upon entering and during the course of the study,
5. Any adverse event(s) that might have occurred (in addition to the Visit CRFs and/or Adverse Device Effect CRF and/or Cutera SADE form completed),
6. Results of any diagnostic tests/histology conducted during the study.

B. The following data will be recorded directly onto CRFs:

7. Patient meets study inclusion and exclusion criteria,
8. A record of the treatment parameters, including the date of each RF treatment and any other adjunct therapy, a drawing of the patients abdomen showing the treatment location, and the vial numbers containing control and treatment biopsies,
9. Any protocol deviations,
10. Subject Questionnaire(s),
11. Study related improvement assessments by the investigator or investigator's designee,

12. Treatment-related pain ratings.

C. The following documents will be maintained in the study records:

13. The Investigator or the research staff will check signed informed consent for accuracy and will always keep the original copy of the signed informed consent in the CRF binder.
14. All correspondence with an Institutional Review Board (IRB), the sponsor, or FDA including required reports will also be retained in the study records.
15. Records of receipt, use or disposition of the investigational device.

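### Does section 9.3.1 need a stated rule for combining several biopsies taken from one side of the same subject?

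*Combined protocol and SAP*

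**What the plan says.** The design section of the protocol (section 4) gives a floor for sampling: "At least two biopsy samples for each subject will be obtained during the abdominoplasty", made up of "at least one from the treatment area and at least one from the control area". Section 6.3, step 4b, repeats this: "at least one skin biopsy (approximately 10 mm x 10 mm; full thickness) will be taken from the area treated with RF", with a matching minimum for the equivalent untreated area on the other side. Neither section sets a maximum or asks for equal numbers on the two sides.

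Section 9.3.1 plans no hypothesis test. Its only analysis statement is that "The primary efficacy endpoint data will be summarized descriptively for the control and treatment areas". Section 9.2 defines the efficacy set as enrolled subjects who complete the RF session, and adds that "Missing data will not be imputed for efficacy or safety endpoints". Section 9.4 does have a rule for repeated observations, for adverse effects only: "counting will be done by subject, not by event", and for a repeated term "the event will be counted only once, at the most severe and longest duration".

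Two further provisions matter. Under section 6.3 the vials are numbered at random and the histologist is blinded to side. Under section 11.6 the CRF holds a drawing "showing the treatment location, and the vial numbers containing control and treatment biopsies", and histology reports are listed among the source documents.

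**The concern.** The histological comparison is the study's only efficacy endpoint, and with no test planned the descriptive table is the efficacy result. Section 6.2 calls for a single imprint per subject, so several treated samples from one subject are replicates within that imprint and not independent observations. The sponsor evidently saw the repeated-observation problem for adverse effects and wrote a rule for it, while the primary endpoint has none.

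Two analysts could therefore follow section 9.3.1 and produce different tables from the same slides: one counting biopsies, one counting subjects. A rule that calls a side positive if any sample is positive gives more chances to whichever side was sampled more. If that were the treated side, an apparent effect could appear with an inert device. What is at stake is the size of a descriptive contrast, since there is no p-value, error rate or power to disturb.

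**Working it through.** **No plan figure to reproduce.** Section 9.1 bases the sample size of up to approximately 14 on clinical judgement, with no alpha, power, effect size or variance. The only document input below is n = 14. All other inputs are assumed.

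**Reading the sections together.** Section 9.2 fixes who is counted (subjects). Section 4.1.1.1 and the Protocol Summary fix the contrast (treated area against the untreated area on the other side). Section 9.3.1 fixes the display (by area). Together these point to one result per subject and side. A table by biopsy is not excluded, but nothing in the text calls for it.

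**Check 1: by biopsy or by subject.** Suppose 4 of 14 subjects are positive on both sides, 10 are negative on both, and each gives one control biopsy.

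- By subject: 4/14 = 28.6% on each side.
- By biopsy, four subjects giving k treated samples each, the rest one: the denominator is 10 + 4k, which is 18 for k = 2 and 22 for k = 3.
- If those four are exactly the four positives: 8/18 = 44.4% or 12/22 = 54.5%.
- If all four are negative: 4/18 = 22.2% or 4/22 = 18.2%.

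These are extremes. If the number of samples is unrelated to the result, the chance that the four are exactly the positives is 1/C(14,4) = 1/1001. The chance that all four are negative is C(10,4)/C(14,4) = 210/1001 = 21%. The expected number of positives among the four is 4 × 4/14 = 16/14, so the average pooled figure is

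- k = 2: (4 + 16/14)/18 = 5.143/18 = 28.6%
- k = 3: (4 + 32/14)/22 = 6.286/22 = 28.6%

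Pooling then adds scatter but no average bias. A bias needs sample number to follow histology. Samples go into fixative at surgery and are read under blinding, and nothing in the plan creates such a link.

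**Check 2: any-positive rule.** Assume 10% background positivity, no device effect, two treated samples and one control.

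- One sample: 14 × 0.10 = 1.40.
- Two independent samples: 14 × (1 − 0.9²) = 2.66.
- Two samples with within-side correlation 0.5: the chance that both are negative is 0.81 + 0.5 × 0.09 = 0.855, so 14 × 0.145 = 2.03.

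Here there is a real bias, 2.0 to 2.7 against 1.4 of 14. It needs unequal counts and an any-positive rule together. With equal counts both sides have the same expectation, and the null contrast is zero.

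**Check 3: a worst-score rule moves the other way.** Assume 80% necrosis and 20% dermal or epidermal damage per sample, necrosis in any one sample suffices, damage in any sample fails the side, and everything is independent. The number of treated sides passing is 14 × (1 − 0.2^k) × 0.8^k = 8.96, 8.60 and 7.11 for k = 1, 2, 3. These are treated-side figures only, with no control contrast. They show that the direction depends on the rule.

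**Check 4: cost of the alternatives.** A per-side mean keeps its expectation for any k, but dilutes a focal change and needs a scale that can be averaged. A single designated sample per side, with no back-up, loses pairs to unreadable specimens. At assumed rates u of 5% or 10%, 14 × (1 − u)² = 12.6 or 11.3 full pairs remain, against 14 × (1 − u²)² = 13.9 or 13.7 when two per side are read and either will do.

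**The case for a change.** The best case for a change is that it costs a few sentences in section 9.3.1, touches no procedure, and would remove an analyst's freedom over the only efficacy table. Equal counts do not remove that freedom either. At an assumed 30% positivity per sample and two independent samples, an any-positive rule gives 14 × (1 − 0.7²) = 7.1 positive sides and an all-positive rule gives 14 × 0.3² = 1.3. Section 9.4 shows that the sponsor knows how to write such a rule, and blinding does not supply one.

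The factual part stands: the readable text has no combining rule, and with more than one biopsy per side the summary depends on the rule chosen. The step to a required change does not. The plan states no rule that gives a wrong answer, and one biopsy per side leaves nothing to combine. A mean, a worst score and a designated sample are all defensible, and the choice depends on the histology scale, which the readable text does not define. The mean may not be computable for narrative reports, and it can hide the dermal or epidermal damage that the endpoint requires to be absent. Section 9.4's most-severe rule would point a different way from a mean. Fixing one rule without the scale would express a preference more than correct an error.

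**Conclusion.** No change is called for. Section 9.3.1 is silent on replicates within a side, and that silence is a matter of detail. A competent analyst would report by subject and side, in line with the subject-based efficacy set and the side-to-side endpoint, and with about 14 subjects could list every reading. The CRF vial numbers and the histology reports allow counts per side and any alternative tabulation to be rebuilt.

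The effect is zero with one biopsy per side. Pooling by biopsy is unbiased on average if sample number is unrelated to histology. Only unequal counts combined with an any-positive or similar rule produce a systematic shift, about 0.6 to 1.3 subjects of 14 in the example (2.03 − 1.40 and 2.66 − 1.40). The plan states neither condition, so no size or direction can be attached to this study.

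This rests on the readable text. Part of section 4 is redacted and the Appendix 1 schedule is not shown, so a fixed number of biopsies could stand there. Section 6.1 also assigns subjects to a subgroup that the readable text does not explain, whereas the examples treat all 14 as one group.

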9.4 Safety Analyses

Device-related and procedure-related adverse effects (AEs) and subjects who prematurely terminate from the study due to an adverse device effect, including the treatment-related pain ratings, will be tabulated and analyzed. For a given AE term, counting will be done by subject, not by event, i.e. for a subject reporting the same AE more than once; the event will be counted only once, at the most severe and longest duration. The number and percentage of subjects experiencing each AE Term will be descriptively summarized. Subject pain ratings during treatment will also be summarized descriptively.

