7.1.4 Unanticipated Serious Adverse Device Effect (USADE/UADE)

An unanticipated serious adverse device effect (USADE) is any SADE on health or safety or any life-threatening problem or death caused by, or associated with the device, if that effect, problem, or death was not previously identified in nature, severity, or degree of incidence in the investigational plan, informed consent, operator manual, other risk analysis documentation, or regulatory application; or any other unanticipated serious problem associated with a device that relates to the rights, safety, or welfare of subjects.

In subjects, the ADEs/SADEs include the effects related to the investigational medical device (clinical study device), the comparator or the procedures involved. For device users or other persons (other clinical staff in the treatment room) ADE/SADE is restricted to the effects related to investigational medical devices. ADEs/SADEs may include the effects (1) resulting from insufficient or inadequate instructions for use, deployment, installation, or operation, or any malfunction of the investigational medical device; or (2) resulting from user error or from intentional misuse of the investigational medical device.

Figure 1. Flowchart for classification of adverse device effects [19]

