7.2 Recording Adverse Device Effects

All potential ADEs will be evaluated and must be recorded in the subject's medical chart and in the study case report forms. ADEs will be monitored and tracked from the time of the first RF treatment.

At each contact with the subject, the Investigator will seek information on ADEs by specific questioning and, as appropriate, by examination. ADEs may be observed by the Investigator and/or clinical research staff, elicited from the subject and/or family member or volunteered by the subject. All observed and volunteered adverse signs and symptoms (both expected and unexpected), regardless of severity or frequency, will be recorded in the case histories (medical chart and CRFs). Included in the description should be the nature of the sign or symptom, the date of onset, date of resolution (duration), the severity, whether the event was expected or unexpected (anticipated or unanticipated), the relationship to study treatment or other therapy, the action taken (if any), and the outcome.

All SADEs and UADEs must be reported according to Cutera and IRB requirements.

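### Section 9.4 tabulates only effects judged device- or procedure-related, so events that 7.2 records but that are judged unrelated appear in no planned table, and the influence of attribution cannot be seen.

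*Combined protocol and SAP*

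**What the plan says.** The safety endpoint (Section 4.1.2) is the incidence and severity of adverse device effects, including pain during RF treatment. Section 7.1.1 defines an adverse device effect as one related to the investigational device. Section 9.4 plans to tabulate "Device-related and procedure-related adverse effects (AEs) and subjects who prematurely terminate from the study due to an adverse device effect", with pain ratings. It counts by subject within each term: "for a subject reporting the same AE more than once; the event will be counted only once, at the most severe and longest duration". It plans no table of events regardless of relationship.

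Section 7.2 sets a wider net for recording: "All observed and volunteered adverse signs and symptoms (both expected and unexpected), regardless of severity or frequency, will be recorded in the case histories". Each entry carries onset and resolution dates, severity, expectedness, action, outcome and "the relationship to study treatment or other therapy". On who gathers this, the section says "the Investigator will seek information on ADEs by specific questioning and, as appropriate, by examination".

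The meaning of *procedure* varies. Section 7.1.1 refers to the device only. Section 7.1.4 says that in subjects "the ADEs/SADEs include the effects related to the investigational medical device (clinical study device), the comparator or the procedures involved". Section 8.1 introduces Table 3 as risks of the device or of the treatment procedure. Section 9.4 uses the word without a definition.

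**The concern.** Whether an event is counted depends on a judgement of relatedness. Section 4 describes the setting: "This is a single-center, prospective, non-randomized, open-labeled study in approximately 14 subjects". The control is an untreated area of the same abdomen, which serves the histology but gives no comparison group for adverse events. Only the histologist is blinded (Section 6.3), and no independent review of relatedness is described.

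An event wrongly judged unrelated would lower the reported incidence and leave no trace in the planned output. Section 9.3.1 rules out formal testing, so the descriptive table, with the pain summary, is the whole safety result. The judgement may be hardest for late findings: participation lasts up to 3 months (Section 4.2), and Table 3 includes nodules, contour abnormalities and textural changes expected to last more than a month.

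There is also a smaller question of definition. Under the wording of 7.1.4, effects of the biopsy, which is taken during abdominoplasty, could enter the same table as RF effects.

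**Working it through.** The plan gives no rate, test or power figure for safety, so there is no figure to reproduce. The check compares sections and then gives the scale.

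**1. From recording to reporting.** Section 7.2 records all signs and symptoms whatever their cause, with relationship as a data item. Section 9.4 reports the device- and procedure-related ones. The difference, events recorded and judged unrelated, is in the CRFs and in no planned table.

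**2. Who decides.** The investigator seeks the events (7.2), the study is open-label (Section 4), and no adjudication is described. That the investigator makes the relatedness call is inferred; no sentence assigns it.

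**3. Scale.** Inputs: n = 14 (Section 9.1, approximate), and the assumption that all 14 start RF treatment and so enter the safety set (Section 9.2). If a term occurs in k subjects and in a of them is judged unrelated, the table shows (k − a)/14 in place of k/14, a difference of a/14.

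- a = 1: 1/14 = 7.1 percentage points.
- a = 2: 2/14 = 14.3 percentage points.

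The step is larger if fewer than 14 start treatment. For one event with k = 1, attribution decides whether the term appears at all. Exact (Clopper-Pearson) two-sided 95% intervals for the two possible tables are:

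| Shown | Estimate | 95% interval |
|---|---|---|
| 0/14 | 0% | 0 to 23.2% (upper limit 1 − 0.025^(1/14)) |
| 1/14 | 7.1% | 0.2% to 33.9% |

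The intervals overlap heavily, so one reattributed subject does not change what the data can statistically exclude by much. What changes is what the reader is told was seen.

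**4. Could surgical effects enter the table?** Four points in the documents bear on this.

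- Biopsies come from tissue that the abdominoplasty removes anyway (Section 4).
- On the surgery day, adverse device effects are recorded at step 3 and the biopsy is step 4 (Section 6.3).
- That day is the last visit (Section 4.2), and follow-up of reported effects ends at resolution or at the end of participation (Section 7.3).
- Table 3 gives pain an expected duration limited to the procedure, which fits the RF session, and has no entry specific to biopsy or surgery.

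Entry is possible under 7.1.4, but the planned assessments leave little room for it.

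**5. Counting rule.** Section 9.4 counts a term once per subject at its worst, with no stated split by attribution. If a device effect and a biopsy effect shared a term in one subject, they would merge at the worse grade. Step 4 makes this unlikely.

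**The case against.** The strongest reply is that 9.4 does what the endpoint asks. The endpoint is adverse device effects, these are related by definition, and the table reports them. That stands: a reader might infer that 9.4 contradicts the endpoint or discards endpoint data, and the documents do not support it.

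A second reply is that attribution is not arbitrary here. Many Table 3 terms are local skin effects, and the single imprint is photographed for location (Section 6.2). Blinding the operator of a one-sided treatment is hardly feasible. This limits the likely size of any bias, but it does not make the excluded events visible.

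A third reply concerns surgery. A reader might infer that bleeding, swelling or infection from the abdominoplasty will inflate the rates. The documents do not support that as a main concern: abdominoplasty is an entry condition and not a study treatment, 7.2 lets an event be related to other therapy, and the timing in 6.3 and 4.2 puts most post-operative events after the last planned assessment. What remains is that one word is used in different senses.

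Finally, 7.1 points is the step for any event in 14 subjects, a true device effect included. It is not evidence of bias. Nor can it be set against Table 3's frequency labels, which have no numerical definition in the documents.

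**Conclusion.** The point holds as a limitation of the safety summary. Reported incidence can be biased down by attribution, and the planned output does not let a reader judge the extent. Nothing in the documents shows that it will be biased, and the direction and size are unknown in advance. The sensitivity is 7.1 percentage points per subject per term, assuming all 14 are in the safety set.

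The conclusion rests on three readings: that 9.4 lists all the planned adverse-event tables, that the unblinded investigator decides relatedness, and that no adjudication takes place because none is described. That device- and procedure-related effects will share one percentage is also a reading, from the single label and the once-per-term rule; 9.4 does not say so outright. Contamination by biopsy or surgical effects is possible and probably small. The study's validity is not in question, and no sample size or endpoint needs to change.

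**What to change.** In Section 9.4:

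1. Keep the adverse device effect table as the summary of the endpoint.
2. Add a table of all recorded adverse signs and symptoms with onset from the start of RF treatment to the start of surgery, regardless of attribution, by subject and term, with the related subset shown beneath each term.
3. Reconcile *procedure* across 7.1.1, 7.1.4, 8.1 and 9.4 so that in the adverse device effect table it means the RF treatment procedure.
4. List any event with onset from the start of surgery separately, biopsy effects included, with its recorded relationship.

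The cost is one extra descriptive table, one short listing and a consistent definition. Onset date and relationship are already recorded under 7.2. Sorting by onset avoids the need for a separate biopsy category of attribution; for events that begin on the day of surgery, the record must show whether onset came before or after surgery started, because 7.2 asks for a date only. Visits and sample size are unchanged. The all-event figures may look less favourable than the related-only ones.
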